Provider experience: In Year 5, we will interview up to 10 providers including clinical officers who prescribed ADT, as well as psychosocial counsellors who led PM+ sessions. In addition to discussing perceived strengths and weakness of the intervention and its implementation, we will also discuss the training and supervision process, as well as provider job satisfaction and burnout.

Patient experience: A random sample of 20 participants (10 male, 10 female) will be interviewed after their final study assessment to assess their experiences with the intervention – including logistical aspect of participation, impact on personal mental health and wellbeing, as well as changes in relationships at the household level.

Sample Size

We assumed $n=30$ enrollees per facility (total $n=420$) during each three month “step”, based on an estimated 10% depression prevalence in Malawi.^{7,84} We further assumed loss to follow-up of 15%, based on intervention trials we have conducted in similar settings.^{11,85}

The power calculation is based on the model described in the analysis section (see below) and a two-sided null value of no effect.⁸⁶ To indicate the precision of the study design, we report “minimum detectable effect” sizes across the range of our primary outcomes at 80%

power, with a type I error rate of 0.05, and conservative intraclass correlation coefficient (ICC) of 0.05, a cluster autocorrelation coefficient (CAC) of 0.80, and an individual autocorrelation coefficient (IAC) 0.80. Table 2 reports these effect sizes.

Analysis of Intervention Effects

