The data from the trial will be analyzed using a generalized linear mixed model framework, which is standard for stepped-wedge cluster designs.^{87,88} The patients participating form an open cohort with repeated measures, as it will be possible to link each patient taking a PHQ-9 screening and any subsequent exams over time. The models will be at the patient-level, nested within clinic-months and clinics. The primary outcomes are: (i) prevalence of depression; (ii) depression severity (PHQ-9 score) conditional on having depression; (iii) WHODAS score conditional on having depression; and (iv) utility score (0 to 1) from the EQ-5D-5L. The first outcome is a dichotomous event for if the patient has depression or not, while the remaining outcomes are treated as continuous. For the principal analysis of the trial, we used the “complete” stepped-wedge of data from months 1 to 18; long-term follow-up will constitute a secondary analysis.

We specify the following model for patient $i = 1, \dots, N$ in clinic $j = 1, \dots, J$ at time period $t = 1, \dots, T$:

$$y_{ijt} \sim F(g(\eta_{ijt}))$$

$$\eta_{ijt} = \mu + x'_{ijt}\beta + z'_{jt}\gamma + \delta D_{(i)jt} + \theta_i + \alpha_j + \phi_{jt} + \tau_t$$

where y_{ijt} is the outcome, $F(\cdot)$ is an appropriate likelihood and $g(\cdot)$ is a suitable link function, x_{ijt} and z_{jt} are respectively patient and clinic level covariates, τ_t are monthly fixed effects, and $\theta_i \sim N(0, \sigma_\theta^2)$, $\alpha_j \sim N(0, \sigma_\alpha^2)$, and $\phi_{jt} \sim N(0, \sigma_\phi^2)$ patient-, clinic-, and clinic-time random

effects term. We will take both intention to treat (ITT) and per protocol approaches. For the ITT analysis, the variable D_{jt} is an indicator equal to one if cluster j is in the intervention state at time t and zero otherwise, thus δ represents our estimated treatment effect. For per protocol analysis D_{ijt} will be a patient-level variable equal to one if the clinic was in the intervention state and the patient completed the treatment as defined above, and zero otherwise. For dichotomous outcomes, we will use a Bernoulli distribution with logistic link function, for continuous outcomes a normal distribution with identity link function. The same models will be used for secondary outcomes.

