There are two main types of approach to dealing with multiple outcomes: multivariate methods and univariate methods. The former method works by jointly modelling all the outcomes at once. However, the joint model of the four outcomes is highly complex, potentially with non-linear sub-models, two-stage models, and shared random effects to allow for correlation (see Appendix), which makes inference difficult or even infeasible without development (and evaluation) of custom software (e.g. a Monte Carlo Maximum Likelihood sampler), which is out of the scope of this project. Instead, we will model the outcomes separately and use a method to correct the family-wise error rate (a univariate methodology).

Statistical model

Aggregate cluster-time outcome

For cluster $j = 1, \dots, J$ at time period $t = 1, \dots, T$ we will screen n_{jt} patients of whom $y_{jt}^{(1)}$ will be diagnosed with depression such that

$$y_{jt}^{(1)} \sim \text{Binomial}(n_{jt}, p_{jt})$$

where we will specify a logistic regression model:

$$\log\left(\frac{p_{jt}}{1-p_{jt}}\right) = z'_{jt}\gamma_1 + \delta_1 D_{jt} + \alpha_{j,1} + \phi_{jt,1}$$

where z_{jt} is a vector of cluster-level covariates, and $\alpha_j \sim N(0, \sigma_\alpha^2)$ and $\phi_{jt} \sim N(0, \sigma_\phi^2)$ are cluster and cluster-time random effects, respectively.

Individual-level outcomes

For patient $i = 1, \dots, N$ who has depression the outcome is $y_{ijt}^{(k)}$ for outcomes $k = 2, 3, 4$. For each outcome we specify the linear model:

$$y_{ijt}^{(k)} = x'_{ijt}\beta_k + z'_{jt}\gamma_k + \delta_k D_{(i)jt} + \theta_{i,k} + \alpha_{j,k} + \phi_{jt,k} + e_{ijt,k}$$

where x_{ijt} is a vector of patient-level covariates $\theta_i \sim N(0, \sigma_\theta^2)$ is an individual-level random effect and e_{ijt} is an independent, identically distributed error term.

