APPENDIX

Multivariate model

Given that the outcomes are mixed discrete and continuous, we will use a shared random effects approach to jointly model the outcomes. For patient $i = 1, \dots, N$ in cluster $j = 1, \dots, J$ at time period $t = 1, \dots, T$ the outcome is $y_{ijt}^{(k)}$ for outcomes $k = 1, 2, 3, 4$. For each outcome we specify the linear predictor:

$$\eta_{ijt}^{(k)} = x'_{ijt}\beta + z'_{jt}\gamma + \delta_k D_{(i)jt} + \psi_{k,\theta}\theta_i + \psi_{k,\alpha}\alpha_j + \psi_{k,\phi}\phi_{jt} \quad (3)$$

where x_{ijt} is a vector of patient-level covariates, z_{jt} is a vector of cluster-level covariates, $\alpha_j \sim N(0, \sigma_\alpha^2)$, $\phi_{jt} \sim N(0, \sigma_\phi^2)$ and $\theta_i \sim N(0, \sigma_\theta^2)$ are cluster, cluster-time, and individual-level random effects, respectively, and $\psi_{k,\cdot}$ are factor loadings with $\psi_{1,\cdot} = 1$ for identifiability. The parameter of interest is δ_k . We will take both intention to treat (ITT) and per protocol approaches. For the ITT analysis, the variable D_{jt} is an indicator equal to one if cluster j is in the intervention state at time t and zero otherwise. Thus, δ represents our estimated treatment effect. For the per protocol analysis, D_{ijt} will be a patient-level variable equal to one if the clinic was in the intervention state and the patient completed the treatment as defined above, and zero otherwise.

For each outcome, $y_{ijt}^{(k)}$, we specify its distribution with probability density function

$$f_k\left(y_{ijt}^{(k)}; \theta, \Phi\right)$$

where $f_k(\cdot)$ is a probability density function, $g_k(\cdot)$ a link function and θ is set of all model parameters and Φ are the random effect terms. For outcome 1 we specify a Binomial-logistic model, and for the other outcomes a linear model with normally-distributed errors.

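### The SAP's model equations leave out the calendar-time effects (and intercept) that the protocol specifies; fitted that way, every ITT estimate absorbs shared time trends

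*SAP*

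**What the plan says.** Protocol, Analysis of Intervention Effects: the linear predictor is "\mu + x'_{ijt}\beta + z'_{jt}\gamma + \delta D_{(i)jt} + \theta_i + \alpha_j + \phi_{jt} + \tau_t". It has an intercept μ and a separate time term τ, and the text explains that "x_{ijt} and z_{jt} are respectively patient and clinic level covariates, τ_t are monthly fixed effects". Time is therefore not part of the clinic covariates z. The principal analysis uses the "stepped-wedge of data from months 1 to 18; long-term follow-up will constitute a secondary analysis". Under Sample Size the protocol adds: "The power calculation is based on the model described in the analysis section".

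SAP, Statistical model: the prevalence model has clinic covariates, the treatment term, a clinic effect and a clinic-time effect. The model for PHQ-9, WHODAS and EQ-5D adds patient covariates, a patient effect and an error term. Neither has an intercept or a time term. The definition given is "where z_{jt} is a vector of cluster-level covariates". The joint model in the SAP Appendix has the same gap: "where x_{ijt} is a vector of patient-level covariates, z_{jt} is a vector of cluster-level covariates".

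The time unit also differs. The protocol's effects are monthly. The SAP's Analysis of Primary Outcomes collects prevalence as totals per step, and the Appendix calls the period quarterly.

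**The concern.** By design, treatment and calendar time are correlated: no clinic is treated in quarter 1 and all are by quarter 6. Without period effects, any change that affects all clinics alike is partly credited to the intervention. The clinic-time random effect does not prevent this, because it has mean zero for each clinic-period and cannot represent a shift common to all clinics.

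At stake are the prevalence odds ratio and the three mean differences. The physical-health secondary outcomes are affected too, since the SAP's Secondary Outcomes section reuses the same specification. The SAP will report estimates and make no claims of significance, so the estimates carry the conclusions. The power calculation rests on a model with a term that the SAP does not state.

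**Working it through.** **Inputs.** Protocol, Study Design and Figure 1: 14 clinics, five arms of 2 or 3 clinics (so 3, 3, 3, 3 and 2 in some order), three-month steps. Analysis window: months 1 to 18, that is six quarters. Protocol, Sample Size: 30 enrollees per facility per step, 15% loss, ICC 0.05, CAC 0.80, IAC 0.80, 80% power, two-sided 0.05.

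The plan's own total reproduces: 30 × 14 = 420. After loss, 30 × 0.85 = 25.5 per clinic-quarter. The protocol's Table 2 of detectable effects is not in the supplied text, so it could not be reproduced.

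**Assumptions.** The quarter marked Int counts as treated. An intercept is fitted. Variance components are known and total variance is 1. IAC is taken at 0.80 and also at 0 (no patient overlap).

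**Hand check.** Number the quarters 0 to 5. A clinic treated from quarter a+1 has control quarters averaging a/2 and treated quarters averaging (a+6)/2. The difference is 3 for every arm. A shared trend of s per quarter therefore shifts each within-clinic contrast by 3s, while comparisons between clinic averages are unaffected. The fitted effect is a weighted mix of the two, so it should fall just below 3s.

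**Generalised least squares on clinic-quarter means.** For n patients per clinic-quarter, the shared variance of a clinic's means is ICC·CAC + (1−ICC)·IAC/n, and the variance specific to each quarter is ICC·(1−CAC) + (1−ICC)·(1−IAC)/n. Ranges cover 25.5 to 30 patients and every position of the two-clinic arm.

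| Case, ICC 0.05 unless stated | Trend absorbed, multiple of s |
|---|---|
| No period effects, IAC 0.80 | 2.96–2.97 |
| No period effects, IAC 0 | 2.85–2.89 |
| No period effects, ICC 0.005–0.02, IAC 0 | 2.5–2.8 |
| No period effects, CAC 0.5–1.0 | 2.75–2.99 |
| No period effects, Int quarter dropped | 3.26–3.45 |
| No period effects, all 30 months | 4.94–4.99 |
| Period effects fitted (six quarters, Int kept or dropped) | 0 |

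The total drift over the window is 5s, so 2.85/5 to 2.97/5, or 57% to 59% of it, ends up in the estimate. With clinics split 3, 3, 3, 3, 2 in arm order, a one-off shared shift after quarter 1 enters at 0.42 to 0.44 of its size, and one after quarter 3 at 0.75 to 0.77.

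**How much drift matters (25.5 per clinic-quarter).** The standard error with period effects is 0.051 SD (IAC 0.80) or 0.081 SD (IAC 0).

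- Bias of one standard error: 5 × 0.051/2.97 = 0.09 SD total drift; 5 × 0.081/2.87 = 0.14 SD.
- Detectable effect at 80% power: 2.80 × 0.051 = 0.14 SD; 2.80 × 0.081 = 0.23 SD.
- Bias equal to that effect: 5 × 0.143/2.97 = 0.24 SD; 5 × 0.227/2.87 = 0.40 SD.

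**Prevalence, assumed illustration.** Let prevalence drift from 10% to 8% with no true effect. The log odds change by ln(0.0870/0.1111) = −0.245, or −0.049 per quarter. Then exp(−0.049 × 2.9) = 0.87. A binomial mixed model with 255 to 300 screened per clinic-quarter gives 0.866 to 0.878 for ICC 0.05 down to 0.005, and 1.00 with period effects.

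**Null simulation.** 400 trials with 99 re-randomisations each, 30 per clinic-quarter, IAC 0.80, assumed trend −0.05 SD per quarter.

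| | Without period effects | With period effects |
|---|---|---|
| Mean estimate (SD) | −0.149 | −0.001 |
| Wald test rejects | 99.8% | 6.5% |
| Re-randomisation test rejects | 5.5% | 6.8% |

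**The case against.** The strongest reply is that the SAP uses shorthand. It also omits the intercept, which nobody would do on purpose: fitted literally with empty covariates, the treatment term would absorb 9–10% (IAC 0.80) or 29–34% (IAC 0) of the overall outcome mean. The clinic covariates carry a time index, so period indicators could sit there. The SAP invokes the standard stepped-wedge framework, and the protocol states the term outright. This may well be the intent, and nothing shows that the term was dropped deliberately. But the protocol uses the same covariate symbol and still lists time separately, and no SAP sentence puts time in the covariates. Software commonly adds an intercept by default; it does not add period effects.

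Second, p-values and confidence intervals come from re-randomisation. This stands: the shared trend is the same under every re-randomisation, so type I error holds. In a further check (600 trials, 399 re-randomisations, trends of 0 to −0.05 SD per quarter), inverting a score-type test without period effects covered the true effect in 92–96% of trials. The damage is to the point estimates. Model-based standard errors serve above only as a yardstick.

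Third, no trend size is documented. This also stands. One possible source for the individual-level outcomes is that patients enter on a positive screen and are then followed, so time since entry can rise in every clinic. Recording these outcomes only at positive screens, and removing enrollees who no longer meet criteria when treatment starts, would blunt that drift.

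Finally, the Appendix model will not be fitted, so correcting it is for consistency only.

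**Conclusion.** The concern holds and should be fixed before analysis. Read as written, the SAP models omit a term that the protocol specifies and the power calculation relies on. With an intercept but no period effects, the ITT estimates take in 2.85 to 2.97 times any shared linear trend per quarter, against zero with period effects. This rests on the six-quarter window, the Int quarter counted as treated, ICC 0.05, CAC 0.80 and IAC between 0 and 0.80; the table shows how it moves otherwise. Whether the bias would be large here is unknown, because the trend is unknown, and a non-monotone pattern could partly cancel. The omission is certain from the text; whether it is shorthand or a real change is not.

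Copying the protocol's term unchanged would not settle it: prevalence totals per three-month step cannot support 18 monthly effects.

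**What to change.** - Write the intercept and fixed period effects into both SAP models, and into the models whose residuals supply the re-randomisation test statistics. If the clinic covariates were meant to hold period indicators, say so.
- Name one time unit per outcome, reconciling the protocol's monthly effects with the step-level prevalence counts and the quarterly period in the Appendix.
- State the months 1 to 18 window for the principal analysis in the SAP, and correct the Appendix model for consistency.

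The cost is SAP wording only; no new data or design change is needed. Model-based standard errors will be larger than those from a model without period effects: at 25.5 per clinic-quarter, about 0.051 against 0.032 SD (IAC 0.80), or 0.081 against 0.052 SD (IAC 0). The larger figures are the right ones for this design and correspond to the model on which the protocol says its power calculation is based.

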Arm 5	Pre	Pre	Pre	Pre	Pre	Pre	Pre	Pre	Pre	Pre	Pre	Pre	Pre	Pre	Pre	Int	Int	Int	Post	Post	Post	Post	Post	Post	Post	Post	Post	Post	Post	Post

Legend: Pre-intervention (light green), Intervention (red), Post-intervention (light blue), 6-month follow-up (medium blue), 12-month follow-up (dark blue)

Footnote: Each arm represents 2-3 health clinics that have been randomized to that particular arm.

A schedule of trial activities is shown in Table 1. Within each cluster, we will use an open cohort design of individual participants who screen positive for potential depression. All attendees at each clinic will be screened at each time point and screen-positive patients will enter the cohort and be followed for the rest of the study—including after initiation of depression care at their site to assess how depression and depression alleviation relate to our primary (depression symptom alleviation; alleviation of functional impairment) and secondary

(HIV patients: viral load; hypertension patients: systolic blood pressure; diabetes patients: A1C or blood glucose levels; all patients: health utility index) outcomes, as well as processes of care (treatment uptake; adherence; perceived mental health stigma). Furthermore, prior to receipt of depression care, as well as six months later, one household member per participant will be interviewed in order to examine changes in their mental and physical health status. A cost-effectiveness analysis will be used to examine the incremental cost of integrated depression care (IC3D) over and above usual care within the IC3 framework.

Randomization, Allocation and Blinding

Health clinics will be randomly allocated to the five arms, the roll-out of which is spaced apart at 3-month intervals, with one exception: 13 potential combinations will be restricted from this algorithm, due to logistical considerations in the geographical layout of Neno District (note that over a quadrillion theoretical permutations are retained). This randomization will be executed by the project principal investigators using a random sequence generator in Stata 15.²⁹

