The Integrated Chronic Care Clinics Depression (IC3D) module draws from best evidence on collaborative care models for depression in low-resource settings.^{40,41} We will use a gold standard, stepped-care approach to offering psychological and pharmacologic treatment across all treatment facilities and clinics. Usual care will be augmented with evidence-based Problem Management Plus (PM+) through provision of manualized, group-based counseling sessions, and antidepressant therapy (ADT) for those with severe depression (or if PM+ is

declined), which is consistent with WHO mhGAP guidelines⁴² for use of ADT. The primary components of the depression care model are described below.

Psychoeducation and treatment selection: If eligible for treatment, the counsellor will inform the client of the availability of PM+ and ADT as treatment options, in addition to encouraging the client to access general supports—such as peer support groups—within Neno. Psychoeducation on depression, treatment course, possible side effects, and benefits of treatment will be provided. Clients will have the autonomy to select their preferred treatment, but the counsellor will encourage clients with moderate depression (PHQ-9 < 15) to consider group-based PM+ counseling given its established efficacy and absence of significant side effect concerns, while adults with moderate-to-severe and severe depression (PHQ-9 ≥ 15) will be encouraged to consider joint ADT and group-based PM+. If the client remains depressed after 12 weeks of receiving either depression treatment modality (as measured by PHQ-9 at quarterly visits), s/he will be offered to switch to or add the other form of treatment.

In the event an enrolled individual no longer meets criteria at treatment initiation, the individual will leave the cohort and not be eligible for treatment but will continue to be evaluated every three months for future eligibility. Given that screening, diagnosis and enrollment will occur at all facilities over the full trial period, we expect any reduction in patients enrolled in the cohort due to lagged treatment initiation will be offset by newly-identified individuals over this same period. This is consistent with an open cohort design for stepped-wedge trials.⁴³

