The parameters of interest are δ_k , which are a (log) odds-ratio for the prevalence outcome and a mean absolute difference in score for the three individual-level outcomes. We will take both intention to treat (ITT) and per protocol approaches for the individual level outcomes. For the ITT analysis, the variable D_{jt} is an indicator equal to one if cluster j is in the intervention state at time t and zero otherwise. Thus, δ represents our estimated treatment effect. For the per protocol analysis, D_{ijt} will be a patient-level variable equal to one if the clinic was in the intervention state and the patient completed the treatment as defined above, and zero otherwise. As we describe below, we will use a randomisation test method to derive exact inferential statistics (p-values and confidence intervals) for the parameters of interest.

Outcomes 2-4 described above are only recorded for those who screen positive for depression at their scheduled visit. Thus, the data do not all cover the full patient population: data for outcomes 2 to 4 are a subset of those for outcome 1. Based on this, we anticipate the data to be normally distributed. However, we will test this assumption by examining QQ plots and conducting KS (Kolmogorov Smirnov) and SW (Shapiro Wilk) tests. In the event the normality assumption is violated, we will consider an alternative specification, such as a two-part semi-continuous model.

Statistical Inference

All models will be estimated separately using restricted maximum likelihood, using the R package lme4. We will report point estimates, confidence intervals, and p-values but not make any claims of "statistical significance", given recent strong arguments against doing so [2].

P-values will be based on the null hypotheses $H_0: \delta_k = 0$ versus the two-sided alternatives $H_1: \delta_k \neq 0$ in each of the models defined above. Given that there are multiple primary outcomes, we will adjust reported p-values for multiple testing using a cluster-based stepdown method, which provides an efficient means of controlling the family-wise error rate [18]. The full methodology is described elsewhere, but we describe it here briefly.

Let there be P hypotheses to be tested H_1, \dots, H_P with associated test statistics T_p . We let the ordered test statistics be:

$$T_{[1]} \geq T_{[2]} \geq \dots \geq T_{[P]}$$

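### The per-protocol model for outcomes 2-4 is an as-treated comparison that can show an effect when there is none, and the promised exact inference is not limited to ITT

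*SAP*

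**What the plan says.** The SAP (Individual-level outcomes) plans both ITT and per-protocol analyses for outcomes 2-4: PHQ-9, WHODAS and EQ-5D utility. In the ITT model, D_jt is the clinic's randomised state. In the per-protocol model, D_ijt is "equal to one if the clinic was in the intervention state and the patient completed the treatment as defined above, and zero otherwise". The Protocol (Analysis of Intervention Effects) uses the same coding, with D equal to one only if the clinic was in the intervention state and "the patient completed the treatment as defined above, and zero otherwise". The SAP Appendix repeats it. Each individual-level model has a patient term that "is an individual-level random effect", plus covariates that are not named.

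Nothing earlier in the SAP defines completion. The Protocol describes PM+ as five weekly sessions but states no threshold for having completed it, and gives no completion rule for antidepressant therapy.

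Immediately after the per-protocol definition the SAP states that "we will use a randomisation test method to derive exact inferential statistics (p-values and confidence intervals) for the parameters of interest". Its Statistical Inference section plans p-values for every model it has set out, and re-randomises clusters only.

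Three further statements bear on the point. The Protocol says that "Clients will have the autonomy to select their preferred treatment". It also says that "screen-positive patients will enter the cohort and be followed for the rest of the study". The SAP says that "Outcomes 2-4 described above are only recorded for those who screen positive for depression at their scheduled visit". The SAP addendum reaffirms ITT as the primary aim, acknowledges refusal, non-attendance and delayed treatment, and adds a CACE analysis by instrumental variable. It does not withdraw or relabel the per-protocol model.

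**The concern.** A per-protocol analysis in the usual sense leaves out patients who departed from protocol. This coding keeps them and moves them to the comparison side. Refusers, patients waiting for treatment and non-completers seen while their clinic is in the intervention state get D = 0, alongside control-period records. Who gets D = 1 then depends on choices and events after randomisation. If those are related to prognosis, the coefficient picks up prognosis as well as treatment.

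The label of exactness is a second problem. Re-randomising clusters justifies a test of the clinic-level indicator. It does not by itself say what a patient's completion would have been in a clinic-period that was really under control. At stake is a biased estimate reported beside ITT for three primary outcomes, with a p-value and interval described as exact.

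**Working it through.** The documents give no figure for the per-protocol analysis. The nearest related figure reproduces: 30 enrollees x 14 facilities = 420 per three-month step (Protocol, Sample Size).

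**Inputs from the Protocol.** 14 clinics in five arms of 2-3 (taken as 3, 3, 3, 3, 2); months 1-18, so six quarters; 30 patients per clinic-quarter; ICC 0.05, CAC 0.80, IAC 0.80. With total SD 1 the variances are clinic 0.05 x 0.80 = 0.04, clinic-time 0.05 x 0.20 = 0.01, patient 0.95 x 0.80 = 0.76 and residual 0.95 x 0.20 = 0.19. The intervention share of clinic-quarters is p = (3x5 + 3x4 + 3x3 + 3x2 + 2x1)/(14x6) = 44/84 = 0.524.

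**Assumptions not in the documents.** Completion share c of 0.5 to 0.8; a prognosis gap g of 0.2 to 0.5 SD between completers and non-completers, or a correlation of 0.1 or 0.3 between non-completion and severity; turnover of 0 to 50% of patients per quarter. The true effect is zero throughout. A negative delta looks like benefit on PHQ-9 or WHODAS.

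**Step 1: closed form, without time or cluster adjustment.** Around the overall mean, completers average -g(1-c) and non-completers +gc. The D = 0 group mixes control records (weight 1-p, mean 0) with intervention-period non-completers (weight p(1-c), mean gc). So

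delta = -g(1-c) - p(1-c)gc/(1-pc) = -g(1-c)/(1-pc).

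At g = 0.35 and c = 0.6: -0.35 x 0.4/(1 - 0.524 x 0.6) = -0.14/0.686 = -0.20 SD. For c from 0.8 to 0.5, g = 0.2 gives -0.07 to -0.14, g = 0.35 gives -0.12 to -0.24 and g = 0.5 gives -0.17 to -0.34.

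**Step 2: the planned model structure.** Period fixed effects (by quarter) and patient, clinic and clinic-time random effects; generalised least squares at the true variances; c = 0.6; 200 to 400 runs per setting. The open-cohort rows also set D = 0 at the entry visit.

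| Setting, no true effect | Mean delta (SD) | Wald rejection, nominal 5% |
|---|---|---|
| Same patients throughout, constant gap 0.2 / 0.35 / 0.5 | -0.016 / -0.028 / -0.036 | 7.5% / 14.5% / 14.5% |
| Open cohort, 0-30% turnover, stable severity, correlation 0.1 | -0.009 to -0.013 | 6-7% |
| Open cohort, 0-50% turnover, stable severity, correlation 0.3 | -0.032 to -0.039 | 14-21% |
| Open cohort, sicker patients complete more, correlation 0.3 | +0.036 to +0.040 | not tabulated |
| Same patients, completers improve faster whether treated or not, gap 0.2 / 0.35 | -0.10 / -0.17 | 79% / 100% |
| Open cohort, 0-30% turnover, completion also tracks current severity, correlation 0.3 | -0.156 to -0.176 | 100% |
| New patients every quarter, gap 0.2 / 0.35 | -0.17 / -0.29 | 94% / 100% |

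At g = 0.5 the faster-improvement setting gives -0.25 and the new-patient setting -0.42. ITT averaged within 0.01 SD of zero in all these settings. REML fits (40 runs, 15% turnover) gave -0.027 (Monte Carlo SE 0.006) for stable severity at 0.3 and -0.166 (0.004) for current severity.

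**Step 3: the entry visit.** Patients join by screening positive, PM+ then takes five weekly sessions, and treatment may slip to the next block. The entry visit therefore has D = 0, and D = 1 can occur only later. Change after entry is partly credited to D even if completion is random. The Protocol allows for untreated improvement ("In the event an enrolled individual no longer meets criteria at treatment initiation", the patient leaves the cohort). Direction is not settled, though: adding the screen-positive recording rule to a simulation with untreated improvement reversed the sign. No size is given for this bias.

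**Step 4: re-randomisation.** In a re-drawn allocation, some clinic-quarters that were under control become intervention, and D_ijt there needs a completion status nobody observed. Rejection with no true effect, nominal 5%:

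- New patients every quarter, gap 0.2: 93% against the cluster-level reference distribution, 14% if only observed completion flags are carried over, 5.5% if every patient's completion type is known.
- Same patients, completers improving faster, gap 0.2: 78%, 1% and 5.5% in the same order.
- Open cohort, 0-30% turnover, completion a fixed patient trait: 4-8%, whether unknown statuses are set to zero, imputed or known.
- Open cohort, 15% turnover, completion tracking current severity at 0.1: 34% if ever-completer status is carried to all re-drawn visits, 7.5% if it is set to zero in quarters really under control. At 0.3: 99% and 65%. The ITT test gave 5.8%.

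**The case against.** The strongest reply is that the plan already handles this. ITT is the primary aim, no significance claims will be made, and the addendum answers non-adherence with a randomisation-based CACE. That stands, and it limits the harm. It does not remove the per-protocol model, which remains in both documents under a label that suggests something else.

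It can also be said that exact inference was meant for ITT only, since the stepdown is introduced for multiple primary outcomes and the permutations rest on cluster randomisation. That is a natural reading, but the text does not say it.

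The sizes are open to challenge too. Stable selection at a correlation of 0.1 gives about -0.01 SD, with rejection not distinguishable from 5% over 300 runs. The Wald tests in the table are not the planned tests. None of the tabulated runs applies the screen-positive recording rule, so they show a mechanism and are not forecasts.

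Several stronger readings are tempting and not supported:

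- A reader might infer that any re-randomisation test of D_ijt must fail. If completion is a fixed patient trait, size stays near nominal even with unknown statuses filled in. Patients whose completion is never observed supply only 0%, 5.7% and 10.7% of re-drawn post-entry intervention visits at 0, 15 and 30% turnover. The 7.5% above is 18 of 240 runs, with an exact 95% interval of 4.5 to 11.6% that includes 5%.
- A reader might infer that the bias flatters the intervention. It reverses if sicker patients complete more, and the entry-visit component has no fixed direction.
- A reader might take the SAP's Missing Data section as evidence that severity will drive non-completion. That section concerns missed appointments; a missed visit contributes no D = 0 record and says nothing direct about completing treatment.

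**Conclusion.** The point holds for the per-protocol model and for the scope of the exact-inference statement. It does not touch the ITT analysis. As coded, the model is an as-treated contrast that can be non-zero under no effect, and the patient random effect removes only part of stable selection. The documents fix neither size nor sign, because they give no completion rate, prognosis gap or turnover. Under the stated assumptions (gaps of 0.2 to 0.35 SD, or correlations of 0.1 to 0.3), the false effect runs from about -0.01 to -0.04 SD in a largely fixed cohort with stable selection to about -0.1 to -0.3 SD with selection on current severity or course, or rapid turnover. The p-value for D_ijt depends on an unstated fill-in rule unless completion is assumed to be a fixed trait. Even where the test's size is right, the estimate stays biased. This should be corrected but is not critical.

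**What to change.** Change the wording in the SAP and the Protocol:

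1. Relabel the D_ijt model as an exploratory, non-randomised as-treated analysis, or drop it. If it is kept, state the completion definition used for analysis, for PM+ and for antidepressant therapy.
2. State that the exact randomisation and stepdown inference applies to the ITT indicator D_jt only.
3. Name the CACE already in the addendum as the treatment-received analysis, with its definition of treatment received and its exclusion restriction written out. Note that, like ITT for outcomes 2-4, it is conditional on screen-positive records.

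No new data or design change is needed. The cost is one of interpretation: the CACE estimates the effect of treatment received rather than of completion, and its interval is wider on its own scale. Its exclusion restriction may not hold exactly, for example because the intervention also encourages use of general supports such as peer groups.
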